After data collection, the collected data will be coded, documented, and analyzed using the Statistical Package for the Social Sciences (SPSS) 19.0 Chinese version software. Both descriptive and inferential statistics will be employed. A significance level of p < .05 will be used to determine statistical significance.

1. Descriptive Statistics:

Categorical variables of demographic data for both experimental and control groups will be presented as percentages, while continuous variables will be described using means and standard deviations.

2. Inferential Statistics:

(a) Independent t-test or Mann-Whitney U test:

Analyze the differences between the experimental and control groups in variables such as balance function, muscle strength, flexibility, cardiovascular capacity, and quality of life befor intervention. A Shapiro-Wilk test will be conducted to check for normal distribution. If the data is normally distributed, an independent t-test will be used; otherwise, the Mann-Whitney U test will be employed.

(b) Chi-Squared Test:

Analyze the homogeneity of basic demographic characteristics (age, gender, education level, marital status), exercise habits, duration of each exercise session, and experience of falling in the past year between the two groups.

(c) Dependent Samples t-test or Wilcoxon Signed Rank Test: Analyze the differences in variables such as balance function, muscle strength, flexibility, cardiovascular capacity, and quality of life within each group 之前 and after the intervention. A Shapiro-Wilk test will be conducted to check for normal distribution. If the data is normally distributed, a dependent samples t-test will be used; otherwise, the Wilcoxon signed rank test will be employed.

(d) ANCOVA Analysis using Intention-to-Treat Analysis:

ANCOVA will be employed to compare the post-test scores between the experimental and control groups while controlling for pre-test scores. This analysis will utilize intention-to-treat principles.

[figure not shown]

Figure 8. Flowchart of the application of virtual reality interactive games

to the lower limb balance of community elders

Research Results

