This study involved the intervention of the experimental group using virtual reality interactive games, while the control group underwent exercise interventions led by original instructors. Both groups participated in modal rate-intensity sessions three times a week for 12 weeks, totaling 36 sessions. Testing was conducted befor and three months after the completion of the program. A total of 84 participants were recruited from two community care activity centers in Taipei City, but 14 participants were excluded due to personal reasons or inability to consistently monitor data due to illness. Ultimately, data from 70 participants who completed at least 30 sessions were analyzed.

Regarding participant attrition, the experimental group initially recruited 35 participants. However, during the 12-week, 36-session program, five participants were absent for over one-third of the sessions (12 sessions) due to health issues or personal preferences, rendering their data unusable. The experimental group experienced a dropout rate of 14.28%. The control group initially recruited 35 participants, but only 33 completed the post-intervention assessment. Two participants were excluded from the analysis due to absence for over one-third of the sessions. The dropout rate for the control group was 8.57%. Both groups had dropout rates within the predetermined range of 15% set befor the study.

The study spanned 36 sessions from February 13th to May 31st, [insert year]. Data from participants who attended less than 12 sessions were

excluded from statistical analysis. Thus, statistical analysis was conducted on data from 30 participants in the experimental group and 33 participants in the control group.

Section 1: Participant Demographics

This study recruited a total of 70 participants, with 35 participants in both the experimental and control groups. Among them, 63 participants completed the entire study, with 30 participants in the experimental group and 33 participants in the control group. The average age of the experimental group (30 participants) was 77.7 years, with the majority being female (96.7%) and married (90.0%). See Table 4-1 for details. Assessment of demographic data in both groups showed no significant differences. Independent samples t-tests or Mann-Whitney U tests and chi-squared tests were used to analyze demographic data, revealing no significant differences between the two groups' demographic characteristics, as shown in Table 2.

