less than 30 minutes	0 (0%)	3 (9.1%)	
more than 30 inutes	22 (73.3%)	15 (45.5%)	
30-60 minutes	8 (26.7%)	15 (45.5%)	
Falls experience in the past			1.034 (0.669)
year			
No falls	23 (76.7%)	25 (75.8%)	
≤3 次	6 (20.0%)	5 (15.2%)	
>3 次	1 (3.3%)	3 (9.1%)	

Table 3 Descriptive Statistics

Section 2: Comparison of Functional Fitness

1. Analysis of Demographic Data

Before the intervention of virtual reality interactive gaming, the participants' functional fitness, including height, weight, lower limb muscle endurance, lower limb flexibility, and agility, were assessed descriptively.

In the pre-test assessment, there were no significant differences between the experimental group and the control group in terms of fitness and quality of life, as indicated by independent samples t-tests, as shown in Table 4.

2. Comparison of Pre-test and Post-test within the Experimental and Control Groups

The results of dependent samples t-tests (Table 5) showed statistically significant improvements in four assessment outcomes in the experimental group, including the 2-minute step test (p < 0.001), left and right chair sit and reach (p < 0.001, p = 0.003), and psychological quality of life (p = 0.008).

In the control group, there was a statistically significant improvement in one assessment outcome, the 30-second chair stand test (p = 0.001).

	Test group (N=30)	Control group	t value (p) or
		(N=33)	Z value (p)
pretest assessment			
BMI	27.0 ± 3.5	25.4 ± 3.8	1.77 (0.077) §
30 seconds sit and stand	16.3±4.6	17.7±5.2	-1.19 (0.234) §
2 minutes to step	96.0±20.7	92.5±25.4	0.60 (0.548)
The seat body bends forward (right)	2.9±10.1	2.6±12.0	0.25 (0.799) §
The seat body bends forward (left)	1.2±11.2	1.4±13.4	-0.08 (0.935)‡
Get up and walk Around at 2.4 meters	8.5±3.2	8.4±3.6	0.70 (0.483) §
Physiological quality of life	10.8±1.4	11.4±1.5	-1.75 (0.086)‡
Psychological quality of life	11.1±1.8	11.7±1.8	-1.28 (0.200) §
Quality of social life	11.2±1.9	11.4±1.1	-0.652 (0.515)§
Environment quality of life	10.6±2.2	10.3±2.0	0.090 (0.928) §

Table 4Functional fitness pre-test of the experimental group and the

control group

[‡] Using independent sample t test

§Using the Mann-Whitney U test

Table 5 Intra-group pre- and post-test comparison between the

experimental group and the control group

		Test g	roup (N=30))		Control	group (N=33	3)
			score				score	

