	protoct	posttast	difference	t value (p)	protost	nasttast	difference	t value (p)
	pretest	posttest	(Pre-test-P	或	pretest	posttest	(Pre-test-P	or
			ost-test)	S value (p)			ost-test)	S value (p)
	Mean ±	standard	deviation	-	Mean ±	standard	deviation	-
BMI	27.0 ± 3.5	26.9±3. 6	0.1±1.0	16.5 (0.741)	25.4 ± 3.8	25.3±3.7	0.1±0.4	75 (0.071)
30 seconds sit and stand	16.3±4.6	17.1±4. 4	-0.9±3.1	-56.5 (0.174)	17.7±5.2	18.5±4.9	-0.8±1.5	-83.5 (0.001)
The seat body bends forward (right)	96.0±20.7	121±25. 7	-26.6±31.2	-4.67(<0.001) §	92.5±25.4	98±20.2	-3.8±15.0	-1.47(0.151) §
The seat body bends forward (left)	2.9±10.1	7.3±9.6	-4.4±7.4	-140 (<0.001)	2.6±12.0	2.9±12.3	-0.3±2.8	0 (1.000)
Get up and walk Around at 2.4 meters	1.2±11.2	5.9±9.6	-4.9±8.1	-3.29 (0.003) §	1.4±13.4	2.9±13.2	-0.2±1.5	-0.79(0.433) §
Physiological quality of life	8.5±3.2	8.3±2.4	0.2±2.9	33 (0.507)	8.4±3.6	8.2±3.4	0.1±0.7	39 (0.384)
Psychological quality of life	10.8±1.4	11.1±1. 4	-0.1±0.4	-1.31 (0.202) §	11.4±1.5	11.3±1.4	0.0±0.1	1.00(0.325) §
Quality of social life	11.1±1.8	11.3±1. 7	-0.2±0.3	-18 (0.008)	11.7±1.8	11.7±1.9	-0.0±0.1	-0.5 (1.000)
Environment quality of life	11.2±1.9	11.3±1. 8	-0.1±0.4	-1.5 (0.500)	11.4±1.1	11.4±1.1	0.0±0.0	_*
The seat body bends forward (right)	10.6±2.2	10.6±2. 2	-0.0±0.1	-1.5 (0.500)	10.3±2.0	10.3±2.0	0.0±0.0	_*

§The Wilcoxon sign test is used, and the rest uses the dependent sample t test.

3. Comparison of Post-test between Experimental and Control Groups

Due to significant differences in demographic data and pre-test assessments between the experimental and control groups, particularly in the education level variable, and considering age as an important control variable, analysis of covariance (ANCOVA) was conducted to compare the post-test scores between the experimental and control groups. Age, education level, and pre-test scores were controlled for in the analysis. Intention-to-treat analysis was used.

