The results of ANCOVA analysis (Table 6) revealed that the post-test scores of the experimental group were significantly higher than those of the control group in five assessment outcomes, including the 2-minute step test (p < 0.001), right chair sit and reach (p = 0.010), left chair sit and reach (p = 0.002), psychological quality of life (p = 0.033), and environmental quality of life (p = 0.048). Additionally, the differences in fitness (except for the 30-second chair stand test) and quality of life had effect sizes (partial eta squared) ranging from 0.011 to 0.267, indicating moderate to substantial intervention effects. These results suggest that the intervention in this study was more effective in improving the aforementioned fitness and quality of life compared to regular community activities.

	StatisticsF /(p)	effect size (partial eta
		squared)
BMI	0.195 (0.661)	0.003
30 seconds sit and stand	0.015 (0.904)	0.000
The seat body bends forward (right)	21.154 (<0.001)	0.267
The seat body bends forward (left)	7.091 (0.010)	0.109
Get up and walk Around at 2.4 meters	10.294 (0.002)	0.151
Physiological quality of life	0.667 (0.418)	0.011
Psychological quality of life	0.956 (0.332)	0.016
Quality of social life	4.766 (0.033)	0.076
Environment quality of life	1.405 (0.241)	0.024
The seat body bends forward (right)	4.080 (0.048)	0.066

Table 6Post-test comparison between the experimental group and the

control group

Note: This analysis uses ANCOVA to control the pretest scores and other significant influencing factors

in the pretest. The control variables include: age, education level, and pretest scores of each variable.

Section 3: Analysis and Comparison of Quality of Life Questionnaire

Upon statistical analysis of pre-test and post-test scores (Table 7), it was found that in the experimental group, there was a difference of 0.4points in the physical domain (p = 0.202), no difference in the psychological domain (p = 0.008), a difference of 0.2 points in the social relationships domain (p = 0.500), and no difference in the environmental domain (p = 0.500). In contrast, in the control group, there was a difference of 0.4 points in the physical domain (p = 0.325), no difference in the psychological domain (p = 1.000), and no difference in the social relationships and environmental domains. The results indicate a significant change in the quality of life in the physical domain for the experimental group.

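### Chapter 4 reports no demographic differences although Table 3 shows two, and the ANCOVA leaves out usual session length unexplained; two quality-of-life results lie too close to 0.05 to be called robust to that choice

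*Combined protocol and SAP*

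**What the plan says.** **Plan (Chapter 3, Section 6).** Item 2(b) plans chi-squared homogeneity tests of basic demographics and, listed after them, of "exercise habits, duration of each exercise session, and experience of falling in the past year between the two groups". The threshold is set once for all tests: "A significance level of p < .05 will be used to determine statistical significance". Item 2(d) names a single covariate: "ANCOVA will be employed to compare the post-test scores between the experimental and control groups while controlling for pre-test scores".

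**Baseline results (Chapter 4, Section 1).** One sentence says, with no table cited and no exception, that the demographic data of the two groups did not differ significantly. The next sentence gives the tests used, "revealing no significant differences between the two groups' demographic characteristics, as shown in Table 2". Table 2 holds age, gender, marriage, BMI, height and weight. Education and usual session length are in Table 3, with p = 0.014 and p = 0.039.

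**Analysis (Chapter 4, Section 2, item 3).** This item justifies the ANCOVA by significant demographic differences, singling out education, and calls age an important control variable. It then states: "Age, education level, and pre-test scores were controlled for in the analysis". The note under Table 6 begins: "This analysis uses ANCOVA to control the pretest scores and other significant influencing factors", and lists age, education and pre-test score. Session length is not mentioned, and its p = 0.039 is not discussed anywhere.

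**The concern.** Three things do not fit together. The unqualified baseline sentence conflicts with Table 3 and with the reason later given for the ANCOVA. The covariate set departs from the plan. The departure also looks selective: age enters at p = 0.080, while session length, for which a homogeneity test was planned and came out below 0.05, stays out with no reason given.

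The variable is plausibly relevant. Sessions in both arms ran for one hour, three times a week, so people used to different session lengths may have had a different change in exercise. At stake are the psychological and environmental quality-of-life claims, which appear in the abstract and in the Chapter 6 conclusion and whose p-values lie just under 0.05.

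**Working it through.** **1. The Table 3 test reproduces.** Session-length counts, in the order printed (the first row is "less than 30 minutes"), are 0 / 22 / 8 in the VR arm (n = 30) and 3 / 15 / 15 in the control arm (n = 33). Band totals are 3, 37 and 23 of 63. Expected counts are 1.429 / 17.619 / 10.952 (VR) and 1.571 / 19.381 / 12.048 (control). The sum of (O − E)²/E is 1.429 + 1.089 + 0.796 + 1.299 + 0.990 + 0.723 = 6.326, as printed. The asymptotic p on 2 df is 0.042 and the exact p is 0.039, so the printed value is the exact one. Education also reproduces: chi-square 11.742, exact p = 0.014.

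**2. The direction cannot be read.** The second band is open-ended above 30 minutes and the third runs from 30 to 60, so they overlap. The only cut that the text supports is at 30 minutes: 0/30 versus 3/33, Fisher p = 0.24.

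**3. Session length was not in the model.** Partial eta squared = F/(F + df). With df = 58, 4.766/62.766 = 0.076 and 4.080/62.080 = 0.066, and the p-values are 0.033 and 0.048; all match Table 6. The analysed set is as described: "63 participants completed the entire study, with 30 participants in the experimental group and 33 participants in the control group". With N = 63, 58 residual df means five parameters. That fits intercept, arm, age, education (as one term) and pre-test score, with no room for session length.

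**4. Distance from the threshold.** The critical t on 58 df is 2.0017 (critical F = 4.007). The proportional fall in the adjusted difference that removes significance, with the standard error held fixed, is 1 − 2.0017/√F. Table 6 row labels are shifted, so outcomes are identified by matching p-values to the text above the table.

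| Result | F | √F | Fall that removes significance |
|---|---|---|---|
| Environmental quality of life | 4.080 | 2.020 | 0.9% |
| Psychological quality of life | 4.766 | 2.183 | 8.3% |
| Right sit-and-reach | 7.091 | 2.663 | 25% |
| Left sit-and-reach | 10.294 | 3.208 | 38% |
| 2-minute step | 21.154 | 4.599 | 56% |

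**5. Illustration of adding the covariate.** Assume that the estimate and residual variance stay the same, and ignore overlap with the other covariates. The R² of arm on session length is 6.326/63 = 0.100, so F is multiplied by about 0.90. Psychological F becomes 4.29 (p about 0.043) and environmental F 3.67 (p about 0.060). Right reach (p about 0.014), left reach (p about 0.004) and the step test (p < 0.001) stay below 0.05. This is not a prediction. If session length explained outcome variance or shifted the estimate, p could move either way.

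**The case against.** The strongest reply is that this is one unlucky baseline test. The abstract reports randomisation, and Tables 2 to 4 contain about 19 distinct baseline tests, so about one p below 0.05 is expected by chance (19 × 0.05 = 0.95). Choosing covariates by baseline p-value is poor practice in any case. A result that is lost at a 1% shift would be fragile to almost any covariate, so its fragility says nothing specific about session length. All of this stands, and it is why session length should not simply replace the present model.

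A reader might also infer two stronger things that the documents do not support.

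- *That the text says session length was balanced.* The sentence quoted from Section 1 is tied to Table 2, where every p is 0.077 or more, and the plan lists session duration apart from basic demographics. The fault lies in the unqualified sentence before it and in the silence about p = 0.039.
- *That the quality-of-life results are confounded by prior exercise.* No association between session length and any outcome is reported. The pre-test score is already in the model, and exercise habits (frequency) did not differ significantly (p = 0.321). Controls covered all three bands, yet Table 7 shows their environmental change as 0.0 ± 0.0 and their psychological change as 0.0 ± 0.0 (p = 1.000), which leaves little or no room for a session-length gradient in that arm. If the open-ended band means more than an hour, the VR arm had the longer usual sessions, and any bias could run against VR.

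It can also be said that the Table 6 note goes on to list its covariates and sets no firm rule of adjusting whenever p < 0.05. That is fair. But then no rule at all explains why age is in and session length is out.

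**Conclusion.** The point holds as one of reporting and robustness. The unqualified baseline statement conflicts with Table 3 on education and session length, and with the later justification of the ANCOVA. The covariate set went beyond the planned pre-test score, and session length was left out without explanation. The psychological and environmental results lose significance if the effect shrinks by about 8% and 1%, so they cannot be called robust to the choice of covariates. The step-test and reach results are much less sensitive, at 56%, 38% (left) and 25% (right).

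This rests on the F(1,58) reading, which the printed statistics support, and on matching outcomes to Table 6 by p-value. Confounding remains a possibility of unknown size and direction. The adjusted result cannot be computed from the documents.

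**What to change.** 1. Correct Chapter 4, Section 1 to state that the arms differed on education and on usual session length.
2. Re-tabulate session length from the raw answers in mutually exclusive bands.
3. Report the planned pre-test-only ANCOVA alongside the model with age and education, and give a reason for the added covariates that does not rest on baseline p-values.
4. Add an ANCOVA with session length, labelled as a sensitivity analysis.
5. If the psychological and environmental findings do not hold across these models, describe them as not robust in the results, abstract and conclusion.

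The cost is small: the data are already collected, and the sensitivity model uses one or two of about 58 residual degrees of freedom. Some p-values may become less favourable.

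### Baseline significance is the stated reason for covariates beyond the pre-test score; it is a poor guide at 30 versus 33 and was not followed consistently

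*Combined protocol and SAP*

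**What the plan says.** Chapter 3, Section 6 plans two sets of baseline tests. Item 2(a) compares the arms on fitness and quality of life before the intervention: "If the data is normally distributed, an independent t-test will be used; otherwise, the Mann-Whitney U test will be employed". Item 2(b) uses chi-squared tests to "Analyze the homogeneity of basic demographic characteristics (age, gender, education level, marital status), exercise habits", session duration and falls. The threshold is common to all: "A significance level of p < .05 will be used to determine statistical significance". Item 2(d) plans an ANCOVA of post-test scores with the pre-test score as the only covariate.

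Chapter 4 reports baseline through these tests. Section 1 describes them as "revealing no significant differences between the two groups' demographic characteristics, as shown in Table 2". Section 2, item 1 says of Table 4: "In the pre-test assessment, there were no significant differences between the experimental group and the control group in terms of fitness and quality of life". No standardised difference or interval is given.

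Section 2, item 3 then justifies the ANCOVA by saying that the arms did differ significantly, in both demographic data and pre-test assessments. It singles out education and adds age because it is considered important. The note to Table 6 states the criterion: "This analysis uses ANCOVA to control the pretest scores and other significant influencing factors". The covariates listed there are age, education and the pre-test score of each variable.

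**The concern.** A baseline p-value depends on sample size as much as on the size of the imbalance, and it says nothing about whether the variable predicts the post-test score. It is therefore a weak basis for choosing covariates, and weaker still in a sample of this size.

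The covariate set also went beyond the plan once baseline data were available, and it does not follow the criterion given for it. A reader cannot tell why one variable entered and another did not. That matters most where a result lies close to the threshold. Two of the five claimed between-arm benefits, psychological and environmental quality of life, have p = 0.033 and p = 0.048, and both reach the Abstract and the Conclusion.

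**Working it through.** **Inputs.** Analysed numbers are 30 and 33 (Chapter 4: "statistical analysis was conducted on data from 30 participants in the experimental group and 33 participants in the control group"). Alpha is 0.05, taken as two-sided because the printed BMI result, Z = 1.77 with p = 0.077, is reproduced only that way. Means, SDs and p-values come from Tables 2 to 4, and F and partial eta squared from Table 6. The row labels of Table 6 do not line up with the text, so I follow the text's matching of p-values to outcomes.

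**Reproducing the printed figures.**
- BMI: pooled SD = √[(29 × 3.5² + 32 × 3.8²)/61] = 3.66. The difference is 27.0 − 25.4 = 1.6, or 1.6/3.66 = 0.44 SD (0.41 to 0.46 allowing for rounding). The t-test gives t = 1.73, p = 0.088, consistent with the printed Mann-Whitney p of 0.077.
- Age: pooled SD = √[(29 × 5.8² + 32 × 8.3²)/61] = 7.22. The difference is 3.3/7.22 = 0.46 SD, with t = 1.81, p = 0.075 against the printed 1.78, 0.080. Rounding explains the gap.
- Education and exercise duration: the Table 3 counts return the printed chi-squares, 11.742 and 6.326. The asymptotic p-values are 0.019 and 0.042 against the printed 0.014 and 0.039. Both are below 0.05 either way.

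**What the tests can see.** The standard error of a standardised difference is √(1/30 + 1/33) = 0.252. With 61 df the critical t is 2.00, so the smallest observed difference that reaches p < 0.05 is 2.00 × 0.252 = 0.504 SD. Power for a true difference of 0.5 SD is 0.496 by the noncentral t and about 0.48 for Mann-Whitney (simulation on normal data). Power of 80% needs a true difference of 0.72 SD.

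**The criterion against the model used.**

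| Variable | Printed p | Standardised difference | Below 0.05? | Covariate? |
|---|---|---|---|---|
| Education | 0.014 | categorical | yes | yes |
| Exercise duration | 0.039 | categorical | yes | not listed |
| BMI | 0.077 | +0.44 | no | only in its own row |
| Age | 0.080 | +0.46 | no | yes |

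Other non-significant differences are physical quality of life −0.41, psychological quality of life −0.33, height −0.32, chair stand −0.28 and weight +0.21. The rest are 0.15 or less in absolute value.

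**Was BMI in the model?** Error df = F(1 − η²)/η². The 2-minute step result gives 21.154 × 0.733/0.267 = 58.1, psychological 4.766 × 0.924/0.076 = 57.9, and environmental 4.080 × 0.934/0.066 = 57.7. Rounding of η² allows 57.9 to 58.2, 57.5 to 58.4 and 57.3 to 58.2, so the integer is 58 in each case. The listed model uses 5 parameters (intercept, group, age, education as one term, pre-test score), and 63 − 5 = 58. The df agree with the note's list and leave no room for BMI as a further covariate.

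**The two statements about baseline.** Section 1 refers to Table 2, which omits education, so its demographic claim can partly be squared with item 3. The pre-test claim cannot: no row of Table 4 is below 0.05, yet item 3 cites significant pre-test differences.

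**The case against.** Four points on the other side carry weight.

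- **The analysis does not rely on the arms starting alike.** A reader might infer that the between-arm claims rest on declared comparability. Item 3 of Section 2 says the reverse: it adjusts because it holds that the arms differed. This point stands, and what remains is the contradiction between the two statements.
- **BMI was not shown to be screened out by its p-value.** Age entered without significance and exercise duration stayed out despite it. Section 6 contains no covariate screen; only the Table 6 note words one. This stands too, and it moves the fault from the screen itself to a stated criterion that does not explain the model.
- **Most listed imbalances are already handled.** Age is in the model, and each fitness and quality-of-life pre-test score is the covariate for its own outcome. BMI, exercise duration and body size remain.
- **Bias from BMI is not demonstrated.** In Table 7 no control participant's environmental score changed, and the mean psychological change in controls is 0.0, so no BMI-related drift is visible. Assuming a partial correlation of 0.1 to 0.5 between BMI and an outcome (not in the documents), the shift would be 0.44 × 0.1 = 0.04 to 0.44 × 0.5 = 0.22 outcome SD, direction unknown. Even that uses the raw imbalance, whereas the relevant one is conditional on age, education and pre-test score and is not reported.

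The power figure also needs care. If allocation was random, as the Abstract says, the population difference is zero by design, and power describes only how blunt the test is. The 0.504-SD limit on observed differences does not depend on that argument.

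**Conclusion.** The point holds as a fault in how baseline is described and how covariates are justified. Significance testing at 30 versus 33 passes every observed difference below about 0.50 SD and has about even odds of detecting a true 0.5 SD. The stated criterion does not account for the covariates used: two variables with nearly equal imbalance were treated differently, and a significant one is not listed. The plan named only the pre-test score, and Chapter 4 contradicts itself on whether pre-test differences were significant.

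Two stronger readings are not supported. One is that omitting BMI biased the quality-of-life results: that needs a BMI–outcome relation and a conditional imbalance that the documents do not give. The other is that the sample cannot exclude imbalances up to about 0.9 SD, from the upper end of the BMI interval (−0.07 to 0.94). The imbalance in the analysed sample is observed, at 0.44 SD; the interval concerns a population difference.

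What can be said is that the environmental result (F = 4.080 against a critical value of about 4.01 on 1 and 58 df) has almost no room for a change of model, and the psychological result (F = 4.766) has little. Whether either crosses 0.05 needs participant data. The figures assume two-sided tests and that the text, not the Table 6 row labels, identifies the outcomes.

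**What to change.** - In Section 6, items 2(a) and 2(b), replace the baseline significance tests with observed standardised differences.
- In the Table 6 note, delete the significance criterion. Use one covariate set for every outcome and justify it on prognostic grounds.
- Report the planned ANCOVA (pre-test score only) beside the age-and-education model. Add a sensitivity analysis with BMI and exercise duration, labelled post hoc because both were singled out after their imbalance was seen. It should inform the reading of the planned analysis, not overrule it.
- If the psychological or environmental quality-of-life result crosses 0.05 between models, describe it as sensitive to covariate choice in the Results, Abstract and Conclusion.
- Reconcile Chapter 4, Section 1 and Section 2, item 1 with Section 2, item 3 and with Table 3.

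The cost is rewording and a re-run of Table 6 on data already collected. In the sensitivity model, BMI takes one residual df (58 to 57) and exercise duration, with three categories, up to two more (to 55). Intervals may widen slightly.
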